Peer support: Therapeutic groups are a mainstay of addiction treatment because they offer drug users, who are often socially isolated, validation and support from others with similar experiences. The behavioral specialist will facilitate conversation about current opioid use, goals for recovery, and triggers for relapse. We anticipate this will take 20-25 minutes.

Medical Management: Each visit will end with guided relaxation and meditation as a way to calm any heightened emotions from group interactions. The physician will write prescriptions for BMT and address individual concerns (e.g., changes in buprenorphine dosage). Because group medical visits will replace most individual visits, focused histories and physical exams may be necessary and could occur in a private room as needed. If more attention is required for acute symptoms an individual visit can be scheduled at the CHC.

Interaction between primary care physicians (PCPs) and research team: The protocol for communications with referring PCPs will be as follows: 1) G-BMT participants will sign a treatment agreement stating that they will attend group visits weekly and all medication refill requests will go to the group physician; 2) the group physician will send electronic medical record (EMR) messages to the PCP with updates to the treatment plan following each group visit; 3) participants will continue to see their PCP for acute medical care, but not for BMT during the study period; and 4) the group physician will transfer care back to the PCP following completion of the G-BMT intervention through an in-person conversation. The treatment agreement (see appendix), which includes patient and provider expectations, and specifies that all prescriptions will be written at BMT group medical visits, will be discussed at the first group visit and signed by both patients and the G-BMT physician. Subsequently, PCPs will be asked to read and sign the agreement as well. Because this study is developmental, deviations from the agreement (e.g. asking the PCP for a prescription refill following a missed group visit) will be recorded as an outcome for future adaptations to the protocol.

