Treatment as usual: Participants randomized to TAU will continue to receive BMT from their PCPs based on a standardized BMT intensification protocol. Prior to the study, PCPs at the CHC will receive one hour of training on BMT intensification. The protocol will require that all BMT patients with persistent opioid abuse receive at least monthly visits with urine drug tests collected at each visit. For participants randomized to TAU, PCPs will receive an automated e-mail reminder about the following protocol. After one urine drug test is positive for opioids, PCPs will increase the frequency of visits to twice monthly with referral for behavioral counseling. After two consecutive positive tests, PCPs will increase visit frequency to weekly. After three consecutive positive tests, PCPs will refer to an addiction specialist or opioid treatment program. We will measure frequency of BMT visits, referral for behavioral counseling and referral to opioid treatment programs during the study. We will determine *observed intensity* of BMT (defined below) for exploratory analyses of treatment outcomes.

Participant tracking: To facilitate tracking participants over the 16 week follow-up period we will use tracking procedures that we developed to retain drug users in our previous research studies, in which we have had an 85% retention rate over 6-month follow-up. On Locator Forms, we will record information about: 1) participants' address and phone number; 2) contact information of participants' family members, friends, case managers, physician, pharmacy, and drug treatment program; and 3) locations where participants hang out.

Data sources and measures: A complete list of measures is listed in Table 1.

Urine Drug Testing: Research visits will include urine drug test collection, which will be used for the primary outcome (both G-BMT and TAU participants will have an equal number of research visits and urines). Urine drug tests collected during G-BMT and TAU medical visits (*clinical drug tests*) will be used for secondary outcomes.

Testing will include opiates, oxycodone, buprenorphine, methadone, cocaine, and benzodiazepines.

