Questionnaire: ACASI technology, which plays an audio recording of questions as it displays the question on a computer screen, will be used by the RA to administer questionnaires. After completing the trial, participants and providers will be assessed for satisfaction with treatment. Interviews will take 30-60 minutes depending on the study visit.

Qualitative Interview: We will conduct 20 in-depth semi-structured interviews with persons who have completed the G-BMT intervention in order to better understand the impact of the group buprenorphine maintenance treatment. Interviews will be audio recorded. Interviews will take 45-60 minutes to complete.

Medical records: We will extract electronic medical record data, including visit and prescription information, from Montefiore's health center to assess *medication and visit adherence, treatment retention* (see below) and to determine the *observed intensity* of BMT, defined as the number of medical or counseling visits attended during the study period for the TAU arm and the number of group visits attended for the G-BMT arm.

Intervention Materials: The RA will also attend group visits to assess fidelity using a checklist derived from the intervention manual. The RA will document completion of each G-BMT component, time spent on components, and use the checklist to rate facilitators on fidelity to the intervention. The RA will also record participants' attendance, completion of self-assessment forms, and engagement in intervention activities (e.g. # of times gave personal updates). Group cohesion will be measured as part of the ACASI interviews. All group visits will be audio-recorded and at least 25% of recordings will be reviewed by the PI to confirm the assessment of intervention fidelity.

Post-intervention Questionnaires:

Patient Satisfaction: We will adapt a previously published questionnaire that assesses satisfaction with BMT in primary care.¹⁰⁰ Satisfaction is measured in three areas: overall satisfaction, staff expertise/ responsiveness, and helpfulness of treatment. We will adapt the helpfulness domain to address specific components of the G-BMT intervention (e.g. self-assessment forms), and add items that assess privacy and confidentiality.

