Provider Satisfaction: We will adapt a previously published questionnaire to assess acceptability of the intervention to participants' PCPs. Satisfaction will be measured in three areas: overall satisfaction with BMT, perceived effectiveness of BMT intensification and support for BMT at the CHC.¹⁰¹ We will add items for PCPs with patients randomized to the G-BMT intervention to assess satisfaction with communications with the G- BMT team and likelihood of referring patients to group-based BMT in the future.

Table 1. Timing and delivery of intervention and study measures

Measure	Study Instrument	Domain	Assessment Period (week)
Urine			
Opioid use	Observed urine	-	All [†]
Questionnaires			
Sociodemographic information	BHIVES Study ⁸²	-	0
HIV Risk Behaviors	AIDS risk inventory ⁹³	-	0, 8, 16
Self-reported drug use	Addiction Severity Index ⁹⁴	-	All
Depression	CES-D ⁹⁵	-	0, 8, 16
Self-efficacy	DTCQ-8 ⁹⁶	Self-efficacy	0, 8, 12, 16
Social Support	MSPSS ⁹⁷	Outcome Expectation	0, 8, 12, 16
Buprenorphine Knowledge	10 item questionnaire	Knowledge	0, 8, 16
Quality of Life	SF-12 ⁹⁸	-	0, 8, 16
Group cohesion*	GCQ-S ⁹⁹	-	2, 4, 8
Medical Records			
Medical Visits	-	-	1-16
Buprenorphine prescriptions	-	-	1-16
Referrals	-	-	1-16
Opioid use	Clinical urine		1-8
Retention in care	-	-	0, 12, 24
Intervention Materials			
Chronic Health Conditions	-	-	0
Self-assessment forms	Check-list	Goals	1-8
Intervention fidelity	Check-list	-	1-8
Post-intervention Questionnaires			
Patient satisfaction	PCBSS ¹⁰⁰	Barriers and Facilitators	8
Provider satisfaction	5 item questionnaire ¹⁰¹	-	8
Qualitative Interviews*	Interview Guide		8

*only collected for intervention arm; [†]Study visits (2,4,6,8,12,16 weeks) CES-D = Center for Epidemiologic Studies Depression Scale; DTCQ-8 = Drug-Taking Confidence Questionnaire, 8 item version; MSPSS = Multidimensional Scale of Perceived Social Support; SF-12 = SF-12 Health Survey; GCQ-S = Group Climate Questionnaire – Short Form; PCBSS = Primary Care Buprenorphine Satisfaction Scale

Analysis:

Main outcome variables:

Primary outcome (efficacy): we will use a dichotomous measure (yes/no) of *opioid abstinence* based on 30-day self-reported opioid use following completion of the intervention and the results of urine drug tests (opiates, methadone, oxycodone) at the 8 and 12 week research visits (see Figure 1). Missing urine drug tests will be considered to be positive for opioids.

Secondary outcomes (efficacy):

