Analysis: We will use mixed effects logistical regression models incorporating different correlation structures between study arms to account for clustering by group in the intervention arm and by PCP in the TAU arm. For the primary outcomes, abstinence will be the dependent variable and study condition will be the main independent variable. Models will include key covariates that are not equally distributed between study arms.

For each secondary outcome, we will construct a separate mixed effects linear or logistic regression model. In other exploratory analyses, we will determine whether changes in perceived social support or self-efficacy, or the *observed intensity* of BMT mediate the association between study condition and abstinence by using interaction terms for key variables and study condition.

Qualitative Analysis: Analytic Plan. Using NVivo software, analysis of qualitative data will be conducted using a modified grounded theory approach. We will develop a coding scheme that reflects the themes that emerge upon iterative reading of the transcriptions. In grounded theory, themes are not specified prior to analysis, but our modified approach will use the framework of Social Cognitive Theory to organize the themes. With the first 3-5 interviews, preliminary codes will be developed independently by [name] and the RA. Using the constant comparative method, additional readings of the transcriptions will lead to consolidation of these coding schemes until no further refinement is required. Coding discrepancies will be resolved by consensus. Once coded, these themes will be organized into a conceptual model explaining the impact of group buprenorphine maintenance treatment.

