Data entry method: At enrollment, the RA will administer interviews using ACASI technology. Interview data will be directly entered on a lap top computer, which will be password protected, and will contain only participant study ID (no other identifying information). Additional data (e.g. urine drug test results) will be entered into a password-protected Redcap database by two separate, trained data entry staff, and discrepancies will be corrected by [name] based on source documents.

Data analysis plan: We will use mixed effects logistical regression models incorporating different correlation structures between study arms to account for clustering by group in the intervention arm. For the primary outcomes, abstinence will be the dependent variable and study condition will be the main independent variable. Covariates will include depressive symptoms and sociodemographic variables that are associated with the study condition in bivariate testing. For each secondary outcome, we will construct a separate mixed effects linear or logistic regression model with similar adjustments. In other exploratory analyses, we will determine whether changes in perceived social support or self-efficacy, depressive symptoms, or intensity of the intervention (i.e. # of group sessions attended) mediate the association between study condition and abstinence by using interaction terms with these variables and study condition. We will also determine whether sub-groups of patients (e.g. those with low perceived social support) benefit most from group participation.

QUALITY ASSURANCE

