Continuing BMT despite ongoing opioid abuse: Participants with three consecutive urine drug tests that are positive for opioids during group medical visits will be offered facilitated referral to methadone maintenance treatment program; however, some may refuse referral. In the G-BMT intervention arm, the research team will meet to discuss the risks and benefits of continuing BMT and participation in group medical visits. In the TAU arm, continuation of BMT will be up to the prescribing physician. If there is concern that risks of continuing treatment outweigh the potential benefits, the participant will be removed from the trial and referred to an

addiction specialist.

Burden of BMT intensification: We will collect data on adherence to medication and visits as a feasibility measure, and we will monitor treatment, after 50% of the sample has accrued.

Potential benefits for participants: Group visits have the potential to improve rates of opioid abstinence thereby reducing HIV risk behaviors and overdose risk. Our preliminary work on buprenorphine group visits has demonstrated that they are highly valued, therefore, other benefits, such as reductions in depressive symptoms or distress, may lead to improved health status.

Collection of AEs and SAEs: Because the research visits will include computerized interviews and urine collection, and the G-BMT intervention will include group counseling and buprenorphine education, participants are likely to incur no more than minimal risk of AEs. However, if AEs occur, they are likely to include psychological distress. AEs will be collected by members of the research team as they conduct research visits or group visits, and will be reported to [name] either immediately (for serious AEs) or during regular weekly project meetings (for non-serious AEs). Serious AEs could include death, life-threatening adverse reaction, inpatient hospitalization, persistent disability, or an event jeopardizing the participant's health.

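### Mediation is to be judged by arm-by-variable interaction terms, which test moderation, and treatment intensity is described differently in the two analysis sections (exploratory analyses only)

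*Combined protocol and SAP*

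**What the plan says.** The method appears twice in the combined protocol and SAP.

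- Section III, Analysis: exploratory analyses will determine whether changes in perceived social support or self-efficacy, or observed intensity, "mediate the association between study condition and abstinence by using interaction terms for key variables and study condition".
- Section IV, Data analysis plan: the same method, with depressive symptoms added and intensity put differently, asking whether "intensity of the intervention (i.e. # of group sessions attended) mediate the association between study condition and abstinence by using interaction terms" with study condition. The next sentence is a separate item: "We will also determine whether sub-groups of patients (e.g. those with low perceived social support) benefit most from group participation".

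Intensity is described in two places. Section III, Medical records, has observed intensity "defined as the number of medical or counseling visits attended during the study period for the TAU arm and the number of group visits"; the latter count applies to G-BMT. Section IV counts group sessions and gives no value for treatment as usual (TAU).

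Three other passages bear on this.

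- Section III, Treatment as usual, ties visits to urine results: "After two consecutive positive tests, PCPs will increase visit frequency to weekly". A third consecutive positive leads to referral. Section IV, Trial Safety, adds: "In the TAU arm, continuation of BMT will be up to the prescribing physician".
- Section III, on communication with primary care physicians (PCPs), says of the G-BMT arm that "participants will continue to see their PCP for acute medical care, but not for BMT during the study period", and hands care back to the PCP when the groups end.
- Section III, Main outcome variables: "Missing urine drug tests will be considered to be positive for opioids".

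**The concern.** Mediation asks whether the arm changes the mediator and whether that change in turn alters abstinence. An arm-by-variable interaction asks whether an effect differs by level of the variable. The plan names only the second for the first question. A variable that carries the whole effect could be dismissed, and one that the arm does not move could be called a mechanism.

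For intensity, the variable itself is not settled, and one description makes the planned term redundant. This matters beyond labelling. Under the heading on additional adaptations to the intervention, section III says that analyses of intensity and outcome will inform the ideal number of visits.

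**Working it through.** **Plan's own figure.** Inputs (Power Analysis): 40 per arm, 10% abstinent in TAU, ICC 0.01, groups of 8, 80% power. Design effect 1 + 7 x 0.01 = 1.07; effective n per arm 40/1.07 = 37.4. At two-sided 5% (assumed; the documents state neither alpha nor sidedness), power for 10% against 37% is 0.799 and the detectable rate is 37.1%. The 37% reproduces and does not depend on the mediation text.

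**What the interaction tests.** Let x be arm, m the mediator and e an error with SD 1. Take m = a*x + e and logit P(y=1) = b0 + b1*m. All of the effect passes through m, yet the true coefficient of x*m is zero, so the test can reject only at its own error rate. Conversely, if a = 0 and the x*m coefficient is not zero, m has the same distribution in both arms. The indirect effect is then zero, and the test gains power as n grows.

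**Size, by simulation** (assumed effects, TAU abstinence 10%, 1:1 arms, no clustering, 4,000 trials per setting). Share of trials with a significant interaction under complete mediation:

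| a, b1 (G-BMT abstinence) | n=80 Wald | n=80 likelihood ratio | n=2,000 Wald | n=2,000 likelihood ratio |
|---|---|---|---|---|
| 0.5, 1.0 (15%) | 1.9% | 7.5% | 5.0% | 5.1% |
| 0.8, 1.2 (20%) | 1.7% | 8.0% | 5.4% | 5.7% |
| 1.2, 2.31 (37%) | 0.8% | 10.7% | 4.8% | 5.1% |
| 1.5, 1.45 (37%) | 2.0% | 8.1% | 4.5% | 4.6% |

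The likelihood-ratio figures at n=80 reflect small-sample inflation. A separate run (a = 1, b1 = 1.2, abstinence about 11% and 25%) gave 1.7% for the interaction at n=80. Requiring both the arm-to-mediator and mediator-to-outcome paths to be significant gave 91.8%.

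With moderation and no mediation, the Wald interaction at n=80 was significant in 11% of trials for a coefficient of 0.5. For a coefficient of 1.0 it was significant in 29% if the mediator has no main effect and about 15% if that main effect is 1.0. In a further setting (coefficient 1.5, no mediator main effect, abstinence about 10% and 27%) it was 47%, against 3.3% for the two-path test.

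**Group sessions as intensity.** If sessions s = 0 throughout TAU, then arm*s = s for everyone. The columns [1, arm, s, arm*s] have rank 3 of 4, so the planned term cannot be estimated. Observed intensity as described under Medical records gives rank 4 of 4.

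**The TAU count.** Assume a first visit in week 1-4, monthly = 4 weeks, twice monthly = 2 weeks, full adherence, and counseling not counted. Over weeks 1-16:

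- Always negative: 4 visits.
- Always positive, visits continuing: weeks 1, 3, 4, ..., 16 = 15 visits, or weeks 4, 6, 7, ..., 16 = 12 visits.
- Always positive, visits ending at referral: 3 visits.

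The count therefore partly follows from opioid use. Whether it is higher or lower in users depends on what happens after referral.

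**Expected abstinent participants.** 40 x 0.10 + 40 x p = 18.8 (p = 0.37), 12 (p = 0.20) or 8 (p = 0.10). With three model terms that is 18.8/3 = 6.3 down to 8/3 = 2.7 abstinent participants per term.

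**Missing mediators.** Someone who misses week 8 has no mediator value but has a urine counted as positive. Assume a share q misses week 8 in each arm, and that abstinence needs both urines negative. Complete-case rates are then 10%/(1-q) and 37%/(1-q):

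- q = 5%: 4 of 80 lost, 10.5% and 38.9%.
- q = 15%: 12 lost, 11.8% and 43.5%.
- q = 25%: 20 lost, 13.3% and 49.3%.

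The 15% borrows the 85% six-month retention that the protocol reports for earlier studies. It is not a forecast for this visit.

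**The case against.** The strongest reply is that this is an exploratory analysis in a pilot that admits it may be underpowered and mainly seeks an effect size. That stands, and it limits the weight. It does not rescue the method, because the interaction fails to detect a complete mediator at n=2,000 as well. An arm-by-mediator term can be one component of a mediation model, but the plan describes no other component.

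Some stronger readings are tempting and should not be drawn.

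- A reader might infer that group sessions cannot support any mediation analysis. Only the interaction column is redundant; [1, arm, sessions] has full rank. With sessions zero in TAU, the indirect effect is the G-BMT abstinence rate minus the G-BMT rate at zero sessions. The direct effect is that zero-session rate minus the TAU rate. A large unconfounded simulation recovered 0.195 of a 0.196 total. The real difficulty is that this extrapolates a within-G-BMT dose-response to zero sessions and assumes no confounding.
- A reader might infer that omitting acute-care PCP visits in G-BMT is an error. Those visits are expressly not for buprenorphine treatment (BMT), so leaving them out fits the construct. The real asymmetry is BMT visits to the PCP after hand-back.
- A reader might infer a known bias from the TAU count. Under assumed urine-positivity patterns, with visits given no effect, its correlation with abstinence ran from -0.71 to +0.40 according to the share whose visits end at referral. That fixes neither sign nor size.
- A reader might call the two intensity descriptions a flat contradiction. Their labels differ, they agree within G-BMT, and zero in TAU is an inference. What stands is that they differ and are not reconciled.

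**Conclusion.** The point holds as a minor one, confined to the exploratory mechanism analyses. As written, both sections assign a moderation test to a mediation question and name nothing that would test or estimate an indirect effect. This conclusion follows from the model algebra. The simulated percentages only illustrate it, rest on assumed effects without clustering, and are not this trial's error rates. The moderation percentages in particular depend on the mediator's assumed main effect.

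On intensity, the supportable conclusions are narrower. The two descriptions need reconciling, and the arm-by-sessions term is not estimable if TAU is zero. BMT visits after hand-back go uncounted in G-BMT, and the TAU count is partly a consequence of opioid use in a net direction that the documents do not determine.

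**What to change.** Use one text in section III, Analysis, and section IV, Data analysis plan.

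1. For social support, self-efficacy and depressive symptoms, one at a time: (a) regress the week 0 to 8 change on arm; (b) regress abstinence on arm, that change and its baseline value, with at most one further prespecified covariate.
2. Report indirect and direct effects on the risk-difference scale with intervals, labelled exploratory.
3. State as a limitation that the week 8 urine overlaps the week 8 mediator, and add a sensitivity analysis using the week 12 outcome.
4. State how a missing week 8 questionnaire is handled, and do not rely on complete cases alone. Multiple imputation of the mediator is one option.
5. Keep stand-alone interaction terms for baseline moderators, that is, the subgroup question.
6. Reconcile the two intensity descriptions into one count of BMT-related visits over the same window in both arms, and report it descriptively. Use group sessions for dose-response within G-BMT, with the caveat that attendance may follow from drug use or dropout.

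The cost is SAP wording and a little analysis time; Table 1 already collects these mediators at weeks 0 and 8. Counseling outside the Montefiore record may be missed, and the count should say so. Estimates will stay imprecise with 8 to 19 abstinent participants, and cluster-based intervals are rough with five groups.
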